As of August 2021, Colombia hosts the vast majority of Venezuelan refugees and migrants (UNHCR, 2022). For vulnerable refugees and migrants in Colombia, and especially for women, gender-based violence (GBV) is present during transit and continues in their new homes where xenophobia, lack of accessible and adequate services, lack of safe economic opportunities, and lack of information on access to services, further increase risk. Lack of livelihood opportunities also affect vulnerable refugees and migrants, especially women, with barriers to employment including lack of information; precarious working conditions with lower payments and longer working days with increasing risks of labor exploitation; xenophobia and discrimination; limited access to formal labor markets; lack of access to financial services, among others. To address these issues, we are conducting a randomized-controlled trial (RCT) of HIAS' Entrepreneurship School with Gender Lens (ESGL), a methodology that targets GBV survivors and women at-risk to help them develop business ideas, access needed support for the prevention of and response to GBV, exploitation and trafficking, and improve participants' overall self-reliance. The RCT will be conducted within four cities in Colombia; approximately 80 eligible participants will be enrolled in each city and randomized to a treatment or control arm in a 2:1 ratio. Survey questionnaires will be administered to participants at baseline, eight months following baseline (endline), and 3-4 months after endline. Outcomes of interest include household self-reliance, mental health, empowerment, decision-making, and GBV risk and knowledge.

Background and Rationale

Colombia is a major host of forcibly displaced Venezuelans, currently with approximately 2.5 million vulnerable refugees and migrants. Colombia also has over 6.7 million internally displaced persons (IDPs) due to historical conflicts and violence. For vulnerable refugees and migrants in Colombia, GBV is present during transit and continues in their new homes where xenophobia, lack of accessible and adequate services, lack of safe economic opportunities, and lack of information on access to services, further increase risk.

HIAS/UNHCR's 2022 study found limited availability of shelters and lack of protection services in border areas, placing women at a higher risk of violence by organised crime and drug traffickers. An increase in registered cases of GBV has also been identified as well as a trend in sexual relationships between adult men and VRAM girls and young women, promising economic

stability, or access to regularisation to control their partners, exposing girls and young women to cycles of violence and other negative consequences such as early pregnancy.

Vulnerable refugees and migrants also face psychosocial effects from their migratory experience, such as depression and anxiety and are further impacted by scarce protective resources when arriving in Colombia. This negative impact is more pronounced for GBV survivors due to psychological effects of enduring GBV, including low self-esteem, depression, fear, anguish, guilt, and post-traumatic stress.

Along with existing limitations in local institutional capacity to respond in the protection, health and justice sectors, xenophobia and institutional violence challenge access to services for GBV survivors. At the same time, local authorities lack knowledge on GBV survivors' rights and the required procedures to guarantee appropriate services, indicating the need to strengthen local capacity.

Lack of livelihood opportunities also affect vulnerable refugees and migrants, especially women. HIAS' latest Labor Market and Capacity Assessment identifies numerous barriers to seeking employment, including barriers in terms of regularisation; lack of information; precarious working conditions with lower payments and longer working days with increasing risks of labor exploitation; xenophobia and discrimination; limited access to formal labor markets; lack of access to financial services, among others.

Intervention

HIAS will promote the incubation of businesses through its Entrepreneurship School with Gender Lens (ESGL), a methodology that targets GBV survivors and women at-risk to help them develop business ideas, access needed support for the prevention of and response to GBV, exploitation and trafficking, and improve participants' overall self-reliance. Participants will go through a general business curriculum, work on business plans and learn gender issues and ways to mitigate GBV risks. Upon training completion, participants are eligible to pitch their business idea to a panel of experts and receive \$800 of seed capital. They will also receive follow-up business advisory support for at least six months, focusing on access to markets and finance and building support networks, in order to continue building self-reliance.

The ESGL will include a mental health and psychosocial support module, contributing to participant self-sufficiency, resilience, and empowerment through skills development such as coping skills, problem-solving capabilities, self-esteem, self-efficacy, communication abilities, self-regulation, and leadership, aimed at strengthening their ability to generate dignified livelihoods.

Study objective

This study will conduct a pilot-randomised controlled trial to evaluate the entrepreneurship curriculum. The evaluation has three primary objectives:

1. Evaluate the preliminary effectiveness of the entrepreneurship programming to improve household self-reliance, mental health, and empowerment for households where women members run businesses.
2. Examine the relationship between GBV risk and self-reliance among women refugees in the Colombian migration context.
3. Assess the feasibility and acceptability of the refugee self-reliance index as a measurement tool in programs that strengthen self-reliance pathways for women individuals.

Methodology

Overview

This pilot RCT will be conducted in Cali, Ipiales, Pasto, and Popayan, and will include a control group. Eligible participants will be randomized to the treatment or control arm and the study team will collect data from both the intervention and comparison groups at: 1) the program baseline, 2) the program endline (8 months post-baseline), and 3) follow-up 3-4 months after program completion.

Screening for Eligibility: Inclusion Criteria

Using their database and a pre-screening tool, HIAS will identify potential participants who meet the following criteria: women, at least 18 years of age, at risk of GBV or ever experienced GBV, have a migratory permit (for migrants and refugees), are Colombian or Venezuelan, have been residing in Colombia for at least six months, and have an entrepreneur profile registered with HIAS. Individuals with the targeted characteristics will then be further screened for study eligibility using the Self-Reliance Index (SRI). First launched in 2020, the Self-Reliance Index (SRI) is the first-ever global tool for measuring the progress of refugee households toward self-reliance (Seff, Leeson, and Stark, 2021). Eligible participants must receive a score between 2 and 3.5 on the tool to be included in the study. This range of scores aims to capture women who are vulnerable, but who are in a stable enough situation to develop an income generating activity (meaning that they are not unhoused or in need of urgent humanitarian assistance), while still in need of financial support, training and GBV assistance. If a participant's score on the SRI falls outside of the specified range, they will be ineligible for further inclusion, thanked for their time, and removed from the study. Participants whose score falls within the specified range will be included in the study and further baseline data will be collected including information on mental health, empowerment, and safety.

Subject Recruitment, enrolment and sample size

HIAS will use their database and the pre-screening tool to identify potentially eligible participants for the study. They will aim to identify approximately 90-100 potentially eligible women through

the pre-screening tool. Official enrollment, consenting, and formal assessment of eligibility will be carried out by the research team. Data collectors will obtain written consent from previously pre-screened women prior to administering the SRI. After administering the SRI, data collectors will immediately administer the remaining survey questionnaire modules for participants whose SRI scores fall within the eligible range of 2 to 3.5. Women whose scores fall outside of the 2-3.5 range will be thanked for their time and not assigned to an evaluation arm.

Participants will be recruited from four cities: Cali, Ipiales, Pasto, and Popayan. The study will aim to enrol 80 women in the study within each city, where participants will be randomly assigned to the intervention or control arm at a 2:1 ratio.. As such, 90-100 women will be identified as potential participants through the pre-screening tool to account for ineligibility during the SRI administration phase.

At the time of enrolment, participants will receive a unique study ID. Following enrolment and baseline data collection, participants will be randomly assigned to the control or treatment arm using a random number generator in Stata (a data analysis software). The unique study ID will be used to track participants over time for future points of data collection.

Consent

Prior to data collection, the researcher will explain the study purpose, procedures, potential risks, and safeguards, such as participant confidentiality and referrals for services, where necessary. The researcher will explain that participants may be assigned to take part in the intervention based on randomization but that non-selection for the intervention will not prevent them from later participation in HIAS programs. They will be informed that they may also be provided with a referral for other programs. The researcher will emphasize that participation is completely voluntary and that participants will not be penalized in any way for choosing not to participate. Researchers will also explain and emphasize that participating or not participating in the study is purely voluntary and will have no impact on their access to future HIAS programming. Prospective participants will also be told that they are free to withdraw from the study at any time and to refuse to answer some or all of the questions. Participants will be informed that their data may be used by the research team in the future. The researcher will encourage the interviewee to ask any questions about the study processes before consenting to participate in the study.

Participants may feel compelled to consent to the study in spite of the above-mentioned informed consent procedures. Potential power differentials between the participants and data collectors may result in inadvertent coercion to participate in the study. The research team will carefully analyze the context-specific factors that may result in participant coercion and discuss strategies for ensuring genuine informed consent. Some of the measures that may be used include:

- Build on existing staff experience with informed consent procedures in other projects.

- Intensive staff training on the importance of informed consent and procedures to minimize potential coercion. Such procedures may include careful explanation and repetition of the nature of voluntary consent (e.g., participation in the study will not affect access to services; participants are free to refuse to answer any questions or to withdraw from the study at any time). Participants will also be given time to consider their decision.
- Multiple opportunities for participants to ask questions throughout the informed consent process and subsequent data collection. Researchers will be trained to respond to frequently asked questions or concerns that participants may raise. Close collaboration with HIAS staff to avoid recruiting participants who may be unable to provide assent voluntarily due to mental health or cognitive disability.

Data Collection

Participant data will be collected at three time points: baseline (when participants are first enrolled in the study), eight months post-baseline (upon program completion), and three months following endline data collection (eleven months after baseline). Data collectors will be hired and trained by Los Andes and the RSRI team members using a combination of online learning modules and in-person training, which will cover the study tools, evaluation protocol, humanitarian principles and its current practice, safeguarding policies, Psychological First Aid (PFA) gender and GBV, and research ethics and best practice.

Study Outcome Measures and Ascertainment

Self-reliance:

The Self-Reliance Index (SRI) is the first-ever global tool for measuring the progress of refugee households toward self-reliance (Seff, Leeson, and Stark, 2021). The tool contains twelve domains focused on a household's basic needs, resources, and sustainability. Domains measure conditions and assets that increase the likelihood that refugees will be able to continue meeting their needs in the future. The study participant will respond on behalf of her household. The final self-reliance score may take a value from 1 to 5, with higher scores reflecting greater self-reliance. The tool is available in Spanish and has been previously validated with Venezuelan migrants in Colombia.

Resilience:

The Brief Resilient Coping Scale (BRCS) captures tendencies to cope adaptively with stress. The scale focuses on the tendency to effectively use coping strategies in a flexible and committed manner to actively solve problems despite stressful circumstances (Trejos Herrera et al., 2023).

Women's empowerment

Women's empowerment will be measured using the Women's Multidimensional Empowerment Index, which was developed using the 2015 Colombian Demographic and Health Survey (Rodríguez Guerrero, Nimeh, & Franco Correa, 2021). The index assesses empowerment multidimensionally based on the definition of empowerment proposed by Kabeer (1999) (Resources, domestic decision making, decision making on personal matters, and achievements), while capturing the notion of disempowerment.

Gender-based violence: Three items from the HIAS Knowledge and Perception of GBV risks and Women's Empowerment tool will be used. The HIAS tool was adapted based on other tools used in the Latin American region (cite). The three items pertain to self-reported perceptions of feeling supported by the community, feeling useful, and feeling controlled by one or more people. Responses are on a likert scale.

Ethical considerations

Risks and Benefits

According to Resolution number 008430 of 1993 of the Colombian Ministry of Health and Social Protection, this is "research without risk", which includes: "studies that employ retrospective documentary research techniques and methods and those in which no intervention or intentional modification of the biological, physiological, psychological or social variables of the individuals participating in the study is carried out, including: review of medical records, interviews, questionnaires and others in which no sensitive aspects of their behaviour are identified or dealt with".

The study is expected to carry minimal risk of loss of confidentiality associated with participation in group discussions, which will be minimized by data confidentiality measures and by using verbal informed consent procedures. Individuals have the option to not participate, or if they choose to participate, to decline to answer any question that they do not feel comfortable answering, or to choose to end their participation in the study at any time. We do not anticipate any psychological risk that may result from study participants. All measures will be taken to minimize the risk related to the contracting and spreading COVID-19 among any of the researchers or study participants, following the guidelines of the Ministry of Health and the University.

Safety and Adverse Events

All referral processes will be handled by HIAS as follows.

CASE MANAGEMENT PROTOCOL AND REFERRAL ROUTES

At HIAS, we have developed clear pathways and procedures to prevent, identify, and promptly address the needs of all Persons of Concern (PDI), that is, all participants who are directly or indirectly involved with each of our programs. For HIAS Colombia, it is essential to meet the needs of our beneficiaries, especially those who will be part of the Owning Rights and Protection: GBV Prevention, Mitigation, and Response in Colombia project.

This protocol was created to specify the pathways for care and management of cases and needs that may arise during the implementation of the research and that, in turn, represent a risk to the psychosocial well-being and safety of our participants and their families. For example, cases of PDI who are not selected to participate in the EGV, participants who have been randomly assigned to the control group, and/or participants who receive EGV training and express some type of need for care.

STEPS FOR CASE MANAGEMENT AND REFERRAL ROUTES

The following describes the procedure designed in conjunction with all strategic areas of HIAS, with the aim of providing clarity on the comprehensive case management and referral pathways we regularly implement as an organization to ensure the protection of our beneficiaries and provide an immediate response to their needs.

HIAS has a robust network of services for the population, as well as referral and counter-referral pathways with other humanitarian organizations and institutional entities to ensure the protection of participants.

Chart 1. Procedure for case management and referrals within the SRI-PRM research project

Stage 1. Preparation for a situation or need

The HIAS Colombia team prepares to address the needs of IDPs through actions that promote the appropriate approach and management of cases based on a rights-based, gender-based, and age-based approach, which complies with humanitarian principles and prevents actions that cause harm.

In summary, the following strategies will be implemented:

- HIAS staff will be trained to comply with strict confidentiality standards for case management.
- Clear referral pathways to HIAS services are available, and, if required, external referral pathways will be activated with partner organizations and entities.
- HIAS services are implemented in a coordinated and complementary manner. Constant communication channels will be established between the Economic Inclusion area and other HIAS areas to avoid duplication of care, prevent re-victimization of participants, and facilitate access to services.

Additionally, at HIAS, we work closely with government institutions, partner organizations in the territories, the private sector, and refugee communities, promoting local integration and access to rights and services.

Stage 2. Identification of situations or needs

When needs or situations arise that affect the psychosocial well-being of our IDPs and/or threaten their continued participation in the program, the HIAS Colombia team will be able to respond to the case by activating the corresponding route, depending on whether it is a GBV or MHPSS case.

Likewise, the following strategies will be developed:

- IE Officers and Research Assistants who will be present at the training and data collection spaces will be trained to address any type of situation or need by providing crisis support and Psychological First Aid to individuals experiencing emotional distress, family conflicts, domestic violence, and suicidal thoughts.
- IE Officers will then inform the IDPs about the services available at HIAS (GBV Case Management, Individual Psychosocial Care, and Legal Protection) and will ask each individual if they would like to be referred to any of these services.

Stage 3. Recording the Situation or Need

When participants express a need to be assisted by HIAS professionals, the needs and/or situation assessment process is activated.

Likewise, the following actions will be carried out:

- Internal referral forms will be used to describe the identified situation, the level of risk identified, the priority range under which the case should be addressed, and whether the participant's consent is obtained.
- Once the PDI's consent is obtained, the IE Officer will carry out the referral process to the GBV Case Manager or the MHPSS Officer, using the internal case referral forms provided by the MHPSS and GBV department.
- The MHPSS and GBV services at HIAS Colombia conduct risk and needs assessments to determine the support participants require, as well as to negotiate access to additional services with partner organizations. Should external referrals arise, the GBV Case Manager or the MHPSS Officer will be responsible for making them and following up on them.
- The Economic Inclusion Officer will follow up on referrals and will be in contact with the MHPSS Officer or GBV Manager in charge of providing care to the beneficiary.

HIAS Colombia has developed a matrix of physical and psychosocial risks associated with the implementation of the gender-responsive entrepreneurship school program, and has also implemented risk mitigation actions for each situation.

Stage 4. Response to the situation that occurred or need encountered

4. Respuesta a la situación ocurrida o necesidad encontrada

- Cualquier situación de riesgo o necesidad será canalizada por el Oficial de Inclusión Económica, quien deberá remitir a los Oficiales SMAPS y Gestor de casos VBG según se requiera.
- Los asistentes de investigación deberán comunicar de manera inmediata al Oficial de Inclusión Económica sobre la situación y este deberá activar la ruta interna de remisión correspondiente.

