## 3. Study Sample

Participants were randomized within each of three cities to the treatment or control group. Inclusion was restricted to women scoring between 2.0 and 4.25 on the SRI at baseline. Additional inclusion criteria included: being a woman at least 18 years of age; at risk of or had ever experienced gender-based violence; Colombian or Venezuelan (with a Temporary Protection Permit); resided in Colombia for at least six months; and had an entrepreneur profile assessed through HIAS' profile scanning process.

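### Objective 2 relates GBV risk to self-reliance in a sample cut on the self-reliance score, so a baseline correlation, or a regression with the SRI as outcome, would be attenuated

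*Protocol*

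**What the plan says.** Under Study objective, the Protocol lists as its second primary objective: "Examine the relationship between GBV risk and self-reliance among women refugees in the Colombian migration context". Self-reliance is measured by the SRI: "The final self-reliance score may take a value from 1 to 5, with higher scores reflecting greater self-reliance".

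Entry depends on the same score. Protocol, Screening for Eligibility: "Eligible participants must receive a score between 2 and 3.5 on the tool to be included in the study". SAP, section 3, gives a different band: "Inclusion was restricted to women scoring between 2.0 and 4.25 on the SRI at baseline".

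Written consent comes before the SRI, but only women in range go further: "data collectors will immediately administer the remaining survey questionnaire modules for participants whose SRI scores fall within the eligible range of 2 to 3.5". Women outside the band therefore leave an SRI score and no GBV answers. The GBV measure is three Likert items.

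Entry is also restricted on the other variable: women must be "at risk of GBV or ever experienced GBV".

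On numbers, "The study will aim to enrol 80 women in the study within each city", and "90-100 women will be identified as potential participants through the pre-screening tool to account for ineligibility during the SRI administration phase".

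No analysis is described for Objective 2. The hypotheses in the Protocol's Data analysis section concern intervention effects, and SAP sections 1 and 2 contain no GBV variable.

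**The concern.** Restricting entry by SRI is a reasonable way to define who receives the programme, and it does no harm to the randomised comparison. Objective 2 is a different kind of question: an association between two variables. Selecting on one of them compresses its variance, which shrinks a correlation, and shrinks a regression slope when the selected variable is the outcome. This happens even if GBV risk is measured perfectly.

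The risk is one of interpretation. A weak baseline association could be reported as evidence that GBV risk and self-reliance are not closely linked, when the entry window produced much of the weakness. Because out-of-band women have no GBV data, the full pre-screened association cannot be estimated directly from the data the plan collects.

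**Working it through.** The documents give no correlation, power or precision figure for Objective 2, so there is none to reproduce.

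**Inputs from the documents**
- Bands on the 1–5 scale: Protocol 3.5 − 2 = 1.5 of 4 points (37.5%); SAP 4.25 − 2.0 = 2.25 of 4 points (56%).
- Implied pass rate: 80/100 = 80% to 80/90 = 89%. This reads 90–100 as a per-city figure and treats all losses as SRI ineligibility.
- Enrolment: 80 × 4 cities = 320. The SAP names three cities, which gives 240 at 80 each.

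**Assumptions, not in the documents:** bivariate normality in the pre-screened pool, and a true correlation r of 0.30 (magnitude).

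**Step 1. Attenuation at the implied pass rate.** Let v be the SRI variance in band divided by its variance before screening (truncated normal).
- In-band correlation: r′ = r√v / √(1 − r² + r²v)
- Slope of SRI on GBV, relative to truth: v / (1 − r² + r²v)
- Slope of GBV on SRI, relative to truth: 1

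| Exclusions | Pass rate | v | r′ | SRI-on-GBV slope |
|---|---|---|---|---|
| Both tails equally | 80% | 0.438 | 0.204 | 46% |
| Both tails equally | 89% | 0.598 | 0.236 | 62% |
| Upper tail only | 80% | 0.583 | 0.233 | 61% |
| Upper tail only | 89% | 0.695 | 0.254 | 71% |

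First row worked: 0.30 × √0.438 / √(0.91 + 0.09 × 0.438) = 0.1985 / 0.9744 = 0.204; slope 0.438 / 0.9494 = 0.46.

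**Step 2. The two bands on one assumed distribution.** Simulation with 2,000,000 draws, SRI mean 2.75, SD 0.6, r = −0.30:

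| | No cut | 2–3.5 | 2.0–4.25 |
|---|---|---|---|
| Share kept | 100% | 79% | 89% |
| Correlation | −0.30 | −0.20 | −0.25 |
| SRI-on-GBV slope | −0.179 | −0.079 | −0.121 |
| GBV-on-SRI slope | −0.498 | −0.497 | −0.497 |

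Over assumed means of 2.5–3.0 and SDs of 0.4–1.0, a true 0.30 becomes 0.13–0.26 in the Protocol band and 0.18–0.29 in the SAP band.

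**Step 3. Later waves.** Only the baseline SRI is truncated directly. With an assumed stability of 0.6 and cross-lag of −0.2, the endline correlation is −0.26 (Protocol band) or −0.28 (SAP band), against −0.30.

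**Step 4. The GBV criterion.** The GBV-on-SRI slope is protected from the SRI cut, but not from selection on GBV itself. If that criterion keeps the top 80%, 50% or 30% of the risk distribution (assumed shares), the slope is about 60%, 38% or 28% of its value in an unselected population.

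**Step 5. Power.** Two-sided 0.05, power = Φ(atanh(r)·√(n − 3) − 1.96). A true r of 0.20 falls to 0.134–0.168 across the four rows of Step 1, so 320 in-band women give 67–85%. Using all 4 × 90 = 360 to 4 × 100 = 400 screened women at r = 0.20 gives 97–98%. Most of the gain comes from removing the truncation: 320 women without it would give 95%.

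**The case against.** The strongest reply is that nobody has planned the analysis that would be biased. No wave, outcome or predictor is named for Objective 2. A regression of the GBV item on the SRI would escape the SRI cut under linearity, and later waves are only indirectly restricted. This stands. A reader might infer that the baseline association is biased toward zero whatever is done; the documents do not support that, and the point is conditional on the model and wave chosen.

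A second reply is that the in-band association is the right quantity for eligible women. That is true of that narrower target, but the objective as worded names a wider population.

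Third, the size is soft. The pass rate is a recruitment allowance, the SRI distribution and true correlation are not given, and single Likert items are not normal, so the invariance of the reverse slope is itself approximate. All of this stands, and it limits the figures to illustrations.

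Fourth, a reader might infer that making GBV the outcome recovers the association for refugee women generally. It does not: the GBV criterion selects on that outcome (Step 4).

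Finally, the SAP, dated April 2024, describes inclusion and randomisation in the past tense, so a change at screening may come too late for some or all women.

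**Conclusion.** The concern holds in conditional form. The sample is selected on one of the two variables that Objective 2 relates, out-of-band women give no GBV data, and nothing in either document addresses the consequence. For a baseline correlation, or a regression with the SRI as outcome, a true r of 0.30 would appear as about 0.20–0.25, and the slope would be about 46–71% of its true value, relative to the pre-screened pool. These sizes rest on normality and on the 80–89% pass rate. The direction, under a linear model, does not depend on the exact values. The effect is smaller under the SAP band than under the Protocol band, and smaller at later waves. The further restriction from the GBV criterion cannot be sized from the documents. The randomised comparison is not affected by this point.

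**What to change.** 1. **Where screening is not complete,** change the Protocol's recruitment section so that the three GBV items are asked of every consented woman together with the SRI, before the eligibility cut is applied. Use all of these women in the baseline analysis of Objective 2. This removes the SRI truncation. Cost: three extra questions for roughly 10–20 non-enrolled women per city. It cannot help women already screened.

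2. **Where only in-band women have GBV data,** specify the GBV item as outcome and the SRI as predictor, or use truncated regression with the limits actually applied, once the Protocol and SAP bands are reconciled. Do not report the raw in-band correlation as the answer. Cost: the SAP must add an analysis for Objective 2, which it now lacks, naming the model, direction and wave. Truncated regression is less precise and relies on normality; the GBV-as-outcome slope is only approximately protected with Likert items.

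3. **In either case,** state that the result applies to pre-screened women already at risk of or exposed to GBV, not to women refugees in general. The GBV entry criterion also restricts the association, and neither change corrects for it. Cost: one sentence.
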